The Effect of Intravenous Infusion of Tramadol-ondansetron on Recovery After Caesarean Section (TRON)

NCT05879536

Statistical Analysis Plan

Protocol Number: TRON

Version: 1.5

Date: 20/08/2024

Introduction

This Statistical Analysis Plan (SAP) outlines the statistical methods and procedures to be used for analyzing data from the study evaluating the non-inferiority of intravenous tramadol-ondansetron (TRON) compared to epidural analgesia (AL-EPI) in post-cesarean recovery.

Study Objectives

Primary Objective

- Evaluate the non-inferiority of TRON compared to AL-EPI in terms of global post-cesarean recovery.

Secondary Objectives

- Assess non-inferiority of TRON versus AL-EPI in acute post-cesarean pain control.
- Compare the incidence of adverse effects between TRON and AL-EPI.
- Evaluate the non-inferiority Of TRON compared to AL-EPI in the obstetric quality of recovery.
- Evaluate the incidence of chronic post-cesarean pain between TRON and AL-EPI.

Study Design

Prospective observational cohort study

Study Population

Inclusion Criteria:

- Patients over 18 years old undergoing cesarean section receiving any of the analgesic strategies studied.
- Consent to participate in the study.

Exclusion Criteria:

- Receiving an analgesic medication other than the one mentioned as "routine multimodal analgesia" (either as regular medication or for acute post-surgical pain)
- Medical history that determines the baseline data of the scales and data that we collect (pain or previous disabilities; addiction to drugs, alcohol or drugs; another disease that worsens the quality of life)
- Medical history that conditions the pharmacological effect (allergy, intolerance or atypical reaction to any of the drugs involved in its treatment or possible cross-reactions)
- Contraindication for neuraxial techniques (patient refusal, difficulty in understanding or communication, localized infection, increased intracranial pressure, or other medical criteria)
- Two or more previous caesarean sections
- Difficulty in understanding or communication
- Mother care will not be available to the newborn in the postpartum period for any reason

Endpoints

Primary

Recovery quality measured by the QoR-15 scale at 24 and 48 hours post-cesarean.

Secondary

- Pain levels measured by the Visual Analog Scale (VAS) every 4 hours for 48 hours.
- Adverse effects within 48 hours post-cesarean.
- Obstetric quality of recovery measured by the Obstetric Quality of Recovery-10 (ObsQoR-10).
- Incidence of chronic pain at 90 days post-cesarean measured by the Numerical Rating Scale (NRS).

Randomization and Blinding

This study does not involve randomization as it is observational. Blinding is not applicable.

Sample Size and Power Calculations

The minimum clinically important difference (MCID) of QoR-15 is 8 points, so we used it as the equivalence threshold. [Anesthesiology 2016 Jul;125(1):39-45]. We used data from previous analgesia studies using this tool with an expected mean of 120 points

with a standard deviation of 28.4. [Anesthesiology 2018; 128:598-608]. Therefore, we calculated that 312 patients are needed to conduct this non-inferiority study of tramadol-ondansetron perfusion with an alpha error of 0.05 and a statistical power of 0.8.

Data Collection and Management

Patient data will be collected at baseline, 24 hours, 48 hours, and 90 days post-cesarean. Data will be extracted from the hospital electronic health records.

Statistical Methods

A statistical analysis of the results obtained from the Quality of Recovery (QoR) 15 questionnaire will be conducted. The sequential Visual analog scale (VAS) pain scores, adverse effects, and the need for rescue medication will be analyzed. Additionally, the Obstetric Quality of Recovery-10 (ObsQoR-10) results will be analyzed to validate the Spanish-translated version and define the minimal clinically significant difference (MCID). Finally, the incidence of chronic postoperative pain will be studied by analyzing NRS results and medication use. A p-value of <0.05 is considered significant.

1. **QoR-15:** A mixed linear regression model will be fitted introducing the type of analgesia (TRON vs EPI) and the covariables considered in the model as fixed effects, with the patient as a random effect. The following covariables will be introduced in the model:
 - Weight of the newborn: quantitative variable in Kilograms
 - Breastfeeding: Yes or no
 - Duration of intervention: quantitative variable in minutes.
 - Previous caesarean section: Yes or no
 - Elective, urgent or emergency caesarean section.
 - Extended surgery: tubal sterilization or any other deviation from a standard caesarean section.
2. **Sequential VAS:** Scale from 0-10 repeated every 4 hours. It will also employ a mixed linear regression model, introducing the same covariables as mentioned in the previous section.
3. **ObsQoR-10:** A mixed linear regression model will be fitted introducing the same covariables as mentioned in the previous section.
4. **Adverse Effects:** Count of events as yes/no. A mixed Poisson regression model introducing the same covariables as mentioned in the previous section.

5. **Rescue Medication:** Count of events as yes/no. A mixed Poisson regression model introducing the same covariables as mentioned in the previous section
6. **Chronic Pain at 90 Days:** A Mixed logistic regression model introducing the same covariables as mentioned in the previous section.

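### The SAP sets non-inferiority objectives for pain (VAS) and obstetric recovery (ObsQoR-10) but gives neither a margin nor a rule that could establish non-inferiority

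*SAP*

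**What the plan says.** - **Objective.** Under Secondary Objectives: "Assess non-inferiority of TRON versus AL-EPI in acute post-cesarean pain control". The same list sets a non-inferiority objective for obstetric quality of recovery.
- **Endpoint.** Under Endpoints, Secondary: "Pain levels measured by the Visual Analog Scale (VAS) every 4 hours for 48 hours".
- **VAS analysis.** Under Statistical Methods, item 2: "It will also employ a mixed linear regression model, introducing the same covariables as mentioned in the previous section". Item 3 does the same for ObsQoR-10. Neither item names a margin, a confidence bound, a sidedness, or the time point or summary on which the groups are compared.
- **Decision rule.** The opening paragraph of Statistical Methods has one rule for all analyses: "A p-value of <0.05 is considered significant".
- **Margin.** The only one is under Sample Size and Power Calculations: "The minimum clinically important difference (MCID) of QoR-15 is 8 points, so we used it as the equivalence threshold".
- **ObsQoR-10 threshold.** The opening paragraph of Statistical Methods says that the ObsQoR-10 results of this study will be used to validate the Spanish version and to define that scale's MCID.

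**The concern.** A non-inferiority conclusion needs a stated margin and a confidence bound (or a test against that margin) that excludes a deficit as large as the margin. For VAS and ObsQoR-10 the SAP has neither. The p-value that a mixed model normally reports for the treatment coefficient tests a difference of zero, and that does not answer the objective in either direction. A result with p≥0.05 does not show non-inferiority, and a result with p<0.05 does not exclude it if the deficit is small.

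Two risks follow. A non-significant VAS comparison could be reported as non-inferior pain control, with no controlled error rate behind the claim. Or a margin could be chosen after the results are known, when the choice can decide the conclusion. Pain is a secondary endpoint here, but it is the outcome on which two analgesic strategies compete most directly.

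For ObsQoR-10 the second risk is concrete. The QoR-15 margin is that scale's MCID. If the same approach were taken for ObsQoR-10, the margin would come from the data being tested.

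**Working it through.** **1. The plan's own figure.** Inputs from Sample Size and Power Calculations: margin 8, "with a standard deviation of 28.4", "with an alpha error of 0.05 and a statistical power of 0.8". Assumed: equal groups, true difference 0, no dropout, one-sided alpha.

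n per group = 2 × [SD × (z₁₋α + z₁₋β) / margin]² = 2 × [28.4 × (1.645 + 0.842) / 8]² ≈ 155.8, so 156 per group and 312 in total (unrounded total 311.66).

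This matches: "Therefore, we calculated that 312 patients are needed to conduct this non-inferiority study". Other readings do not: one-sided 0.025 gives 396, two-sided superiority at 0.05 gives 396, and two one-sided equivalence tests give 432 (alpha 0.05) or 530 (alpha 0.025). So a margin-based non-inferiority calculation stands behind QoR-15. An 8-point margin cannot carry over to VAS, which runs from 0 to 10.

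**2. What non-significance would mean for VAS.** The document gives no VAS SD and no VAS margin, so these are assumptions shown as a range: 156 per group, one mean per patient, two-sided 0.05, SD 1.5 to 3.

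SE = SD × √(2/156). For a true disadvantage d, P(non-significant) = Φ(1.96 − d/SE) − Φ(−1.96 − d/SE).

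| Assumed SD | SE | 95% CI half-width | P(non-sig.), d = 0.5 | P(non-sig.), d = 1.0 |
|---|---|---|---|---|
| 1.5 | 0.170 | 0.333 | 16% | <0.1% |
| 2 | 0.226 | 0.444 | 40% | 0.7% |
| 2.5 | 0.283 | 0.555 | 58% | 6% |
| 3 | 0.340 | 0.666 | 69% | 16% |

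These are the chances of missing a real disadvantage. Each becomes a false non-inferiority rate only if non-significance is taken as the criterion and the deficit is at or beyond whatever margin would have been set.

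**3. Why p<0.05 and a margin can disagree.** Take SD 2 (half-width 0.444).
- Observed difference 0.3: the 95% CI is 0.3 ± 0.444, or −0.144 to 0.744. This is non-significant. It would meet a margin of 1.0 and fail a margin of 0.5.
- Observed difference 0.5: the 95% CI is 0.056 to 0.944. This is significantly worse, yet it would meet a margin of 1.0.

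The p-value settles neither case. The margin does, and the document has none.

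**4. What the planned size could support.** Power to show non-inferiority at one-sided 0.025 and true difference 0, same assumptions:

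| Assumed SD | Margin 0.5 | Margin 1.0 |
|---|---|---|
| 1.5 | 84% | >99% |
| 2 | 60% | 99% |
| 2.5 | 42% | 94% |
| 3 | 31% | 84% |

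Whether 312 patients are enough for the pain objective therefore depends heavily on a margin that has not been set. The margins of 0.5 and 1.0 are illustrations, not proposals.

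**The case against.** **The plan never says that p≥0.05 means non-inferiority.** This is correct. A reader might infer from the single p<0.05 rule that a non-significant VAS difference will be declared non-inferior. No sentence says so, and the rule names no null hypothesis and no sidedness. A p-value can also come from a test against a margin, and the reproduced sample size shows that the authors reasoned from a margin for QoR-15. So the misreading is a risk left open by the plan, not one of its provisions, and the rule is undefined for this purpose rather than shown to be wrong. What does not help the plan is that a test against a margin needs a margin, and VAS has none.

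**The protocol may contain the margin.** It is not at hand, so this cannot be excluded. But the SAP itself states the objective, the model, the decision rule and the QoR-15 margin, and it neither gives nor points to a margin for VAS. An objective that its own methods section cannot answer is more than detail left to the protocol.

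**The size is soft.** This also stands. It is tempting to carry over the QoR-15 ratio, 8/28.4 = 0.28 SD, and quote one error rate for VAS. Nothing in the document supports that transfer, which is why only a range on assumed VAS SDs is given.

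**ObsQoR-10 is not the same case.** This is partly right. The SAP does foresee a threshold for that scale, so a threshold is not wholly absent. But it is to be defined from this study's results, and the SAP does not say that it will serve as the margin.

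**Conclusion.** The point stands in this form: the SAP declares non-inferiority objectives for VAS pain and ObsQoR-10, gives a margin only for QoR-15, and does not define how non-inferiority would be concluded for the other two. With the usual test of the treatment coefficient, the planned analysis cannot support those conclusions.

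The documents do not support saying that the sponsor plans to equate non-significance with non-inferiority. The illustrated ranges, 16% to 69% at a true 0.5-point disadvantage and <0.1% to 16% at 1.0 point, rest on assumed SDs, equal groups of 156 and one unadjusted mean per patient. They show that non-significance would be a poor basis for the claim. They do not estimate this study's error rate.

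The sponsor should correct this. It touches secondary claims and leaves the primary sample size as it is.

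**What to change.** Before outcome data are examined:

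1. **VAS.** State and justify a margin in points on the 0–10 scale, the summary or time point of the 4-hourly scores to which it applies, and the confidence level. Claim non-inferiority only if the upper confidence limit for TRON minus AL-EPI from the mixed model lies below the margin.
2. **ObsQoR-10.** Do the same, with a margin not derived from this study's data and the bound taken in the direction of that scale.
3. **If no margin can be justified** for either outcome, restate that objective as estimating the difference with a 95% CI and drop the non-inferiority claim.
4. **In either case**, state that p≥0.05 is not evidence of non-inferiority.

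The cost is SAP wording and the work of justifying the margins. No extra data collection is needed. The downside is that a secondary claim may become descriptive.

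### The exclusion for non-routine analgesia has no time limit, so read literally it can remove women after exposure, and it is not reconciled with rescue medication as an outcome

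*SAP*

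**What the plan says.** Under Study Population, women enter the cohort by the analgesia they get: the inclusion criterion asks for women "receiving any of the analgesic strategies studied". The first exclusion criterion then takes out women "Receiving an analgesic medication other than the one mentioned as 'routine multimodal analgesia' (either as regular medication or for acute post-surgical pain". It has two limbs. Regular medication is a fact known at baseline. Analgesia for pain after surgery is not, and no time point is attached to it.

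The primary endpoint is "Recovery quality measured by the QoR-15 scale at 24 and 48 hours post-cesarean", so the outcome is observed one and two days after the exposure begins. The design is a "Prospective observational cohort study".

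The opening paragraph of Statistical Methods says that "the need for rescue medication will be analyzed", and item 5 of that section gives it a mixed Poisson model ("Rescue Medication: Count of events as yes/no"). Rescue medication is not in the Endpoints list. The SAP does not list the drugs that count as routine or as rescue, which may be left to the protocol. It has no rule on whether a woman given another analgesic after entry stays in the analysis.

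**The concern.** A cohort comparison should select women on facts fixed before the exposure starts. A woman on TRON or AL-EPI who is given a non-routine analgesic at, say, 12 hours meets the literal wording of the exclusion before her QoR-15 is measured. The need for more analgesia follows the exposure, may depend on it, and is plausibly related to poor recovery. Dropping such women makes the remaining group look better than the group that started.

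The primary claim is non-inferiority, so a true deficit in one group that is partly removed by selection is a route to a false positive conclusion. Adjusting for the listed covariates cannot restore the outcomes of women who are no longer in the data. The criterion acts on the whole cohort, so the pain scores and the rescue outcome would be affected too. Two analysts following this SAP could build different cohorts from the same records.

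**Working it through.** **The texts side by side**

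- Exclusion: a non-routine analgesic for pain after surgery, at any time, puts a woman outside the study.
- Statistical Methods: the need for rescue medication is an outcome, so women who need it are expected in the data.
- Both hold together if the exclusion refers only to the regimen planned at entry, or if the rescue drugs count as routine. The SAP states neither. In the second case a woman who needs a drug outside the routine list could still be removed after exposure.

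**The plan's own figure**

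Inputs from Sample Size and Power Calculations: margin 8, SD 28.4, alpha 0.05, power 0.8. One-sided testing, equal groups and a true difference of 0 are assumed, because the SAP does not state them.

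- n per group = 2 × (1.645 + 0.842)² × 28.4² / 8² = 155.8, so 156 per group and 312 in total. This matches the SAP.

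**How much shift matters**

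This takes one unadjusted time point, SD 28.4 and a true difference of −8, where false non-inferiority is 5%.

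- SE = 28.4 × √(2/156) = 3.216.
- Shift that raises 5% to 10% = (1.645 − 1.282) × 3.216 = 1.17 points.
- Removing k women from TRON who average d points below their group mean shifts that mean by k × d / (156 − k).
- For k = 8 (5.1%): SE 3.259, shift needed 1.18, d = 1.18 × 148/8 = 21.9 points.
- For k = 16 (10.3%): SE 3.306, shift needed 1.20, d = 1.20 × 140/16 = 10.5 points.

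**Range under assumed rates**

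Every rate and correlation here is an assumption. Need for extra analgesia is a latent normal trait with correlation r to poorer QoR-15. It affects 20% of AL-EPI, and a share p of the women in need is removed. The mean of those kept rises by p × r × 28.4 × φ(c) / (1 − p × q), where q is the group's need rate and c its cut-off. In TRON, q = 1 − Φ(0.842 − r × 8/28.4), which is 22.4% to 26.0% for r from 0.3 to 0.7.

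| p | Removed, AL-EPI / TRON | Observed difference | False non-inferiority |
|---|---|---|---|
| 0.3 | 6% / 6.7–7.8% | −7.94 to −7.68 | 5.2–6.1% |
| 0.5 | 10% / 11.2–13.0% | −7.89 to −7.39 | 5.4–7.2% |
| 0.8 | 16% / 18.0–20.8% | −7.78 to −6.79 | 5.7–10.1% |

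The error rates use the slightly smaller SD left after removal; with SD 28.4 the top value is 9.6%.

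- Larger gap set by assumption (16% / 23%): at most 13.2% (12.3% with SD 28.4).
- Every woman in need removed, 10% of AL-EPI and 20% of TRON: shift 1.3 to 3.1 points, error about 10–22%.
- Table rates reversed, so that AL-EPI loses more: differences −8.06 to −9.21, error 4.8% down to 2.2%.

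**Equal removal is not always harmless**

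Take q = 20% and p = 0.5 in both groups, so 10% is removed from each. Each mean rises by 0.5 × r × 28.4 × 0.280 / 0.9 = 4.42 × r. With equal r the difference does not move. With r = 0.7 in TRON and 0.3 in AL-EPI it moves by 4.42 × 0.4 = 1.8 points, more than the 1.17 above.

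**The case against.** The strongest reply is that this is an ordinary entry criterion. It stands under Study Population among medical history, contraindications and previous caesareans, and its verb matches the inclusion criterion. No passage tells the analyst to drop an enrolled woman. A rescue model makes sense only if rescued women are in the data. The wording also refers to a regimen that is described elsewhere, so the protocol may settle which drugs are routine.

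Much of this stands. The entry reading is plausible, and the absence of drug lists from a SAP is no error. But nothing in the SAP secures that reading, and the time limit is missing from a rule that the SAP itself states.

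The objection to the size also has force. The rates are all assumed, most of the tied-rate scenarios move the error by only a point or two, and the calculation ignores the covariate-adjusted mixed model that the SAP specifies.

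A reader might go further and infer that rescued women are being dropped, that the rescue outcome is therefore empty, or that the result is tilted towards TRON. The document supports none of these. It reports no removals, its terms are open, and it gives no rate of extra analgesia in either group from which a direction could be read.

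**Conclusion.** The point holds in conditional form and should be fixed, with medium confidence. The exclusion as worded can select women on an event after exposure that is related to QoR-15, and it is not reconciled with the rescue outcome.

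Bias arises if removal is tied to poor recovery and the groups differ either in the rate of removal or in how strongly need relates to QoR-15. If more poorly recovering TRON women go, false non-inferiority becomes more likely; if more such AL-EPI women go, the comparison works against TRON. Equal removal leaves the comparison unshifted only when need relates to QoR-15 equally in both groups.

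The size cannot be derived from the SAP. The 1.17-point tipping value rests on the SAP's SD, margin and sample size together with the one-sided, equal-group, single-time-point assumptions above. The scenario rates show only what could happen.

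**What to change.** - State that the exclusion rests only on facts known before the studied analgesia starts: regular medication, or a different regimen planned at entry.
- Keep every eligible woman who started TRON or AL-EPI in the primary QoR-15 analysis.
- Reconcile the exclusion with the rescue-medication passages, so that non-routine analgesia given later is analysed there, under the protocol's definition of rescue, and is not a ground for removal.
- An analysis without these women may be added as a sensitivity analysis.

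The cost is the wording of one criterion and one sentence on rescue medication, plus a matching protocol change if the protocol carries the same wording. If any woman was removed on this ground after starting, she can be brought back where consent and data allow; the SAP says "Data will be extracted from the hospital electronic health records", but this depends on her QoR-15 having been recorded.

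There are two downsides. Outcome variability rises slightly, and extra analgesia in retained women may itself narrow a group difference, which is the reason for offering the sensitivity analysis. The change concerns the analysis set only, not which analgesics are given.

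### The adjustment set for this non-randomised non-inferiority comparison has no baseline score and no maternal demographic or general-health variable, and no other method for residual confounding is planned

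*SAP*

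**What the plan says.** The primary objective (SAP, Study Objectives) is to "Evaluate the non-inferiority of TRON compared to AL-EPI in terms of global post-cesarean recovery". Under Randomization and Blinding the SAP notes: "This study does not involve randomization as it is observational". The primary endpoint (Endpoints) is "Recovery quality measured by the QoR-15 scale at 24 and 48 hours post-cesarean".

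Under Data Collection and Management, "Patient data will be collected at baseline, 24 hours, 48 hours, and 90 days post-cesarean". The source is the hospital electronic health record. The content of the baseline collection is not listed.

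Statistical Methods, item 1, specifies a mixed linear model with analgesia type and covariables as fixed effects and the patient as a random effect. It then introduces a list with "The following covariables will be introduced in the model". The list has six entries: newborn weight, breastfeeding, duration of surgery, previous caesarean, urgency of the caesarean, and extended surgery. Items 2 to 6 (VAS, ObsQoR-10, adverse effects, rescue medication, chronic pain at 90 days) carry the same list over.

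The other control on prior state is by restriction. The exclusion criteria include "Medical history that determines the baseline data of the scales and data that we collect", with previous pain or disability, addiction, and other disease that worsens quality of life given as examples. They also exclude other analgesic use, history that alters drug effect, and two or more previous caesareans.

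**The concern.** Without randomisation, nothing in the design balances the groups on characteristics that affect recovery. Exclusions and covariables have to do that work, and the SAP names the covariables exhaustively. The list describes mainly the surgery and the obstetric situation. It says nothing about the mother's age, body size or general health, or her score on the scale before analgesia. Breastfeeding is a weak confounder control because it may itself respond to the analgesia received.

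A non-inferiority claim is sensitive to this in both directions. If TRON patients would have recovered better anyway, an inferior treatment can pass. If they would have recovered worse, a treatment that is truly non-inferior can fail. Because the list is reused, the same gap runs through every secondary endpoint.

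**Working it through.** **What the adjustment set covers**

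| Covariable (Statistical Methods, item 1) | What it describes |
|---|---|
| Newborn weight | the infant |
| Breastfeeding | the mother, but possibly affected by treatment |
| Duration of surgery | the operation |
| Previous caesarean | maternal obstetric history, fixed before treatment |
| Urgency | indication, fixed before treatment |
| Extended surgery | the operation |

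Absent from the list: any baseline score, maternal age, BMI and comorbidity. Absent from the whole SAP: propensity score, weighting, matching, or a sensitivity analysis for confounding.

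**Reproducing the sample size**

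Inputs from Sample Size and Power Calculations: margin 8, SD 28.4, alpha 0.05, power 0.8. Assumed, because the SAP does not state them: one-sided alpha, equal groups, true difference zero.

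n per group = 2 × [28.4 × (1.645 + 0.842) / 8]² = 155.8, rounded up to 156. The total is 312, which matches the SAP. One-sided 0.025 would give 396, so the figure corresponds to one-sided 0.05. No stated figure is wrong, but the calculation contains no allowance for confounding.

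**Effect of a residual bias**

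SE of the difference = 28.4 × √(2/156) = 3.22 points.

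- False non-inferiority when TRON is truly 8 points worse and the bias b favours TRON: Φ(b/SE − 1.645).
- Power when the true difference is zero and the same bias goes against TRON: Φ((8 − b)/SE − 1.645).

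| Assumed residual bias (points) | Share of margin | False non-inferiority | Power if bias is against TRON |
|---|---|---|---|
| 0 | 0% | 5.0% | 80.0% |
| 1 | 12.5% | 9.1% | 70.3% |
| 2 | 25% | 15.3% | 58.7% |
| 2.5 | 31% | 19.3% | 52.6% |

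At one-sided 0.025 with the same 156 per group, the false non-inferiority rate goes from 2.5% to 5.0% with 1 point of bias and 9.0% with 2 points.

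**What could produce a bias of this size**

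For a single omitted baseline score with equal SDs at baseline and follow-up, bias = imbalance × baseline-outcome correlation. An imbalance of 2 points with correlation 0.5 gives 1.0; 5 points with correlation 0.5 gives 2.5. Both inputs are assumed. The imbalance meant is what remains after the six covariables and the exclusions. The SE is for one time point without covariates, whereas the planned model uses two time points and six covariables, so its SE will differ.

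**The case against.** The plan is not without protection. Previous caesarean is a maternal characteristic fixed before treatment, urgency is a pre-treatment factor, and both are adjusted for. The exclusions remove patients with prior pain, disability, addiction or disease that lowers quality of life, which is much of the baseline-health difference one would fear. A reader might infer that the model has no maternal covariable at all, or that all baseline imbalance passes into the estimate. The SAP supports neither reading.

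A reader might also infer that a baseline QoR-15 is collected and then ignored. The SAP does not establish that. It names QoR-15 only at 24 and 48 hours, and the baseline collection could be demographics and history. The exclusion wording about baseline data of the scales is a hint, not a schedule. What the baseline visit contains may properly stand in the protocol, which is not available here.

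The SAP also does not say how patients come to receive one strategy or the other, so selection by prognosis is a possibility rather than a documented fact. The imbalance and correlation used above come from no document.

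These points limit the size of the concern and make the baseline-score part conditional. They do not remove it. Restriction cuts off the extremes and leaves the remaining range unbalanced. The adjustment set is fixed in the SAP itself, so its gaps are a matter for the SAP.

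**Conclusion.** The point holds in a limited form. For a non-randomised non-inferiority comparison, the SAP fixes six covariables, uses them for all endpoints, includes no baseline score and no maternal demographic or general-health variable, and plans nothing further against residual confounding. Imbalance that survives the six covariables and the exclusions will bias the primary estimate, in a direction that cannot be known in advance.

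The omission is certain; its size is not. The range of about 9% to 19% false non-inferiority, against a nominal 5%, illustrates an assumed residual bias of 1 to 2.5 points with 156 per group, SD 28.4 and one-sided 0.05. It is not an estimate for this study. It does show that a bias well inside the 8-point margin is enough to matter. The SAP should be changed, but the present plan does not by itself invalidate the comparison.

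**What to change.** In Statistical Methods, item 1, and by extension items 2 to 6:

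- Add, as fixed effects, maternal variables recorded before analgesia starts and available in the baseline data or health record, for example age and BMI.
- Add the baseline value of the scale being analysed wherever it was collected, and state for each scale whether it was. If no baseline QoR-15 exists, say so; the maternal variables can be added regardless.
- Fix the final list before any outcome data are examined, and state how missing covariate values will be handled.
- Do not add anaesthetic technique unless overlap between the groups is confirmed. With an epidural comparator it may come close to determining the treatment group.

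The cost is SAP wording, a few degrees of freedom out of about 312 patients, and possibly some missing covariate values. A baseline score that was never taken cannot be recovered for patients already treated.

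### ObsQoR-10 has a non-inferiority objective but no margin, and the scale's MCID is to be defined in the same cohort, so a margin chosen after the results are known is not ruled out

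*SAP*

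**What the plan says.** Four parts of the SAP bear on this point.

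- **Study Objectives, Secondary Objectives:** "Evaluate the non-inferiority Of TRON compared to AL-EPI in the obstetric quality of recovery". The Endpoints section names ObsQoR-10 as the instrument and attaches no margin to it.
- **Statistical Methods, introductory paragraph:** the ObsQoR-10 results are to be used to "validate the Spanish-translated version and define the minimal clinically significant difference (MCID"). The same paragraph gives the only decision criterion in the SAP, a p-value below 0.05.
- **Statistical Methods, item 3 (ObsQoR-10):** "A mixed linear regression model will be fitted introducing the same covariables as mentioned in the previous section". No margin, confidence bound or order of steps follows.
- **Sample Size and Power Calculations:** "The minimum clinically important difference (MCID) of QoR-15 is 8 points, so we used it as the equivalence threshold". This is the only numerical margin in the SAP. It belongs to QoR-15 and is cited to a published source.

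The Randomization and Blinding section says that blinding does not apply.

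**The concern.** A non-inferiority conclusion means that a confidence bound for the group difference excludes a stated margin. Without a margin, the mixed model yields an estimate and a p-value against zero difference, and neither answers the non-inferiority question. A non-significant p-value does not show non-inferiority. A significant one does not settle the matter either, because a small significant deficit may still lie inside an acceptable margin.

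Someone therefore has to supply an ObsQoR-10 margin. The SAP sets its QoR-15 margin equal to an MCID, and the only ObsQoR-10 MCID it mentions is one to be worked out from this cohort. The study is unblinded, and nothing requires the MCID method or value to be settled before TRON and AL-EPI are compared. An analyst could thus know the group difference when choosing how wide the margin is. At stake is whether the ObsQoR-10 non-inferiority statement can be interpreted.

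**Working it through.** **Step 1: reproduce the plan's own figure.** Inputs from Sample Size and Power Calculations: margin 8, SD 28.4, alpha 0.05, power 0.80. Assumed: true difference 0, equal groups, one-sided alpha.

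n per group = 2 × [SD × (z₀.₉₅ + z₀.₈₀) / margin]² = 2 × [28.4 × (1.645 + 0.842) / 8]², which rounds up to 156, or 312 in total. This matches the SAP. One-sided 0.025 would give 198 per group (396), and a two-sided equivalence test at alpha 0.05 would give 216 per group (432); neither matches. The 312 therefore rests on QoR-15 alone, with one-sided 0.05, and implies nothing about an ObsQoR-10 margin.

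**Step 2: look for an ObsQoR-10 margin.**

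| Element | QoR-15 | ObsQoR-10 |
|---|---|---|
| Non-inferiority objective | yes (primary) | yes (secondary) |
| MCID | 8 points, published source | to be defined from this study's results |
| Margin | 8 points, set equal to the MCID | none stated |
| SD | 28.4 | none stated |
| Confidence-bound rule | none stated | none stated |

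**Step 3: how much the choice of margin matters.** The SAP gives no ObsQoR-10 SD or margin, so everything here is in SD units with assumed margins m. Assumed: 156 per group, one-sided 0.05, and a true deficit of TRON of 8/28.4 = 0.282 SD, borrowed from QoR-15. Repeated measures and covariate adjustment are ignored.

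Standard error of the difference = √(2/156) = 1/√78 = 0.113 SD.

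P(declare non-inferiority) = Φ[(m − 0.282) × √78 − 1.645]

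| Margin m (SD) | Argument of Φ | P(declare) |
|---|---|---|
| 0.2 | −2.37 | 0.9% |
| 0.282 | −1.645 | 5.0% |
| 0.3 | −1.48 | 6.9% |
| 0.4 | −0.60 | 27.4% |
| 0.5 | 0.28 | 61.1% |

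**Reading the table.** Each row treats its margin as fixed. The table does not simulate a margin derived from the data. It shows how far the verdict on one and the same true deficit moves with the margin. A declaration in the lower rows is a false claim only if 0.282 SD is already an unacceptable deficit.

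**The case against.** The strongest reply is that the SAP never links the in-study MCID to the non-inferiority test. The sentence about validation and the MCID states a psychometric aim, and item 3 describes a model with no reference to an MCID. The rule that MCID equals threshold is applied only to QoR-15. This stands. A reader might infer that the SAP prescribes a circular margin and that the test is therefore invalid as planned. The text does not support that; it only leaves the route open.

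Three related inferences also go too far.

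- **That no ObsQoR-10 MCID exists.** The SAP says that this study will define one, in a sentence about the Spanish version. It does not say that no other value is available. The protocol was not available for this review and might fix a margin.
- **That a margin from this cohort removes all control of false claims.** An anchor-based or pooled distribution-based MCID need not depend on the difference between TRON and AL-EPI. The risk lies in choosing the method or value once that difference is known.
- **That power measures the harm.** With no true difference, the chance of declaring non-inferiority runs from 54.8% at 0.2 SD, Φ(0.2 × √78 − 1.645), to 99.7% at 0.5 SD. Those are correct declarations, and power rises with width for any margin, including one fixed in advance.

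It can also be said that this is ordinary missing detail, since the pain objective on VAS is likewise a non-inferiority objective without a margin. That is true. What sets ObsQoR-10 apart is that the SAP itself plans to produce, from the tested data, the kind of quantity it used as a margin for the other scale.

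**Conclusion.** The point holds in a limited form. As written, the SAP provides no working non-inferiority test for ObsQoR-10, and it does not prevent the MCID derived in this cohort from being adopted as the margin after the groups have been compared. That this would happen is an inference from the handling of QoR-15 and from the absence of any other ObsQoR-10 value; the SAP does not state it.

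The size can only be illustrated. Across assumed margins of 0.2 to 0.5 SD, the chance of declaring non-inferiority for a true deficit of 0.282 SD goes from 0.9% to 61.1%. None of these is an ObsQoR-10 figure from the SAP. The issue affects one secondary objective and should be corrected. The 8-point QoR-15 margin and the sample size do not change.

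**What to change.** 1. State that the ObsQoR-10 MCID derived in this study is for future studies and will not serve as the margin in this one.
2. Then do one of the following:
   - Fix a numeric ObsQoR-10 margin from a source independent of this cohort, with its justification, the alpha and the confidence-bound rule, before the groups are compared. If the protocol already contains such a margin, cite it in the SAP.
   - Restate the objective as estimating the TRON minus AL-EPI difference in ObsQoR-10 with a 95% CI, and make no non-inferiority claim.

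The cost is SAP wording only. The validation and MCID work can go ahead as planned. The downside is that, under the second option, one secondary non-inferiority claim becomes descriptive.
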